13.7.3.3. Population Pharmacokinetics

Statistical analysis of the population PK parameter data will be the responsibility of CPMS, Quantitative Sciences, GSK.

Plasma concentration-time data from the groups in Part 2 may be combined with data from dose escalation and further analyzed using a population approach. A nonlinear mixed effect model may be used to determine population PK parameters and important covariates (biomarker, or disease related covariates).

PK data will be presented in graphical and/or tabular form and will be summarized descriptively.

13.7.4. Immunogenicity Analyses

The immunogenicity assessment will include the incidence (confirmed positive results only) and titers of anti-GSK2849330 binding antibodies at any time point post baseline. Full details will be provided in the RAP.

13.7.5. Pharmacokinetic/Pharmacodynamic Analyses

Data permitting, exploratory population covariate PK/PD/biomarker analyses will be provided.

13.7.5.1. Translational Research Analyses

The results of translational research investigations will be reported *in or separately from* the main clinical study report (CSR). All endpoints of interest from all comparisons will be descriptively and/or graphically summarized as appropriate to the data.

Data permitting, the results of secondary translational research objectives will be reported in the main CSR. The results of exploratory biomarker research investigations will be reported separately from the main clinical study report. Full details will be provided in a RAP.

Further details on the translational research analyses will be addressed in the RAP.

13.7.5.2. Novel Biomarker(s) Analyses

The results of these biomarker investigations may be reported separately from the main CSR. All endpoints of interest from all comparisons will be descriptively and/or graphically summarized as appropriate to the data.

Additional exploratory analyses may be performed to further characterize the novel biomarker.

13.7.6. Pharmacogenetic Analyses

Further details on PGx analyses will be addressed in [Appendix 8](#) and the PGx RAP.

14. STUDY CONDUCT CONSIDERATIONS

14.1. Posting of Information on Clinicaltrials.gov

Study information from this protocol will be posted on publicly available clinical trial registers before enrollment of subjects begins.

14.2. Regulatory and Ethical Considerations, Including the Informed Consent Process

Prior to initiation of a study site, GSK will obtain approval from the appropriate regulatory agency to conduct the study in accordance with International Conference on Harmonization Good Clinical Practice (ICH GCP) and applicable country-specific regulatory requirements.

The study will be conducted in accordance with all applicable regulatory requirements.

The study will be conducted in accordance with ICH GCP, all applicable subject privacy requirements, and the ethical principles that are outlined in the Declaration of Helsinki 2008, including, but not limited to:

- IRB/EC review and approval of study protocol and any subsequent amendments
- Subject informed consent
- Investigator reporting requirements

GSK will provide full details of the above procedures, either verbally, in writing, or both.

Written informed consent must be obtained from each subject prior to participation in the study.

14.3. Urgent Safety Measures

If an event occurs that is related to the conduct of the study or the development of the IP, and this new event is likely to affect the study of subjects, the Sponsor, and the investigator will take appropriate urgent safety measures to protect subjects against any immediate hazard.

The Sponsor will work with the investigator to ensure the IRB/EC is notified.

14.4. Quality Control (Study Monitoring)

In accordance with applicable regulations, Good Clinical Practice (GCP) and GSK procedures, the site will be contacted prior to the start of the study to review with the site

staff the protocol, study requirements, and their responsibilities to satisfy regulatory, ethical, and GSK requirements. When reviewing data collection procedures, the discussion will include identification, agreement and documentation of data items for which the eCRF will serve as the source document.

The investigator and the head of the medical institution (where applicable) agrees to allow the monitor direct access to all relevant documents and to allocate their time and the time to their staff to monitor to discuss findings and any issues.

Monitoring visits will be conducted in a manner to ensure that the:

- Data are authentic, accurate, and complete.
- Safety and rights of subjects are being protected.
- Study is conducted in accordance with the currently approved protocol and any other study agreements, ICH GCP, and all applicable regulatory requirements.

14.5. Quality Assurance

To ensure compliance with ICH GCP and all applicable regulatory requirements, GSK may conduct quality assurance audits of the site. Regulatory agencies may conduct a regulatory inspection at any time during or after completion of the study. In the event of an audit or inspection, the investigator (and institution) must agree to grant the auditor(s) and inspector(s) direct access to all relevant documents and to allocate their time and the time of their staff to discuss any findings/relevant issues.

14.6. Study and Site Closure

The end of the study will be defined as the date of the LSLV enrolled.

Upon completion or termination of the study, the monitor will conduct site closure activities with the investigator or site staff (as appropriate), in accordance with applicable regulations, ICH GCP, and GSK Standard Operating Procedures.

GSK reserves the right to temporarily suspend or terminate the study at any time for reasons including (but not limited to) safety issues, ethical issues, or severe noncompliance. If GSK determines that such action is required, GSK will discuss the reasons for taking such action with the investigator or head of the medical institution (where applicable). When feasible, GSK will provide advance notice to the investigator or head of the medical institution of the impending action.

If a study is suspended or terminated for **safety reasons**, GSK will promptly inform all investigators, heads of the medical institutions (where applicable), and/or institutions conducting the study. GSK will also promptly inform the relevant regulatory authorities of the suspension/termination along with the reasons for such action. Where required by applicable regulations, the investigator or head of the medical institution must inform the IRB/EC promptly and provide the reason(s) for the suspension/termination.

GSK may also close study sites which fail to recruit subjects within a predefined timeframe, as defined within the SPM.

14.7. Records Retention

Following closure of the study, the investigator or head of the medical institution (where applicable) must maintain all site study records (except for those required by local regulations to be maintained elsewhere) in a safe and secure location. The records must be easily accessible when needed (e.g., for a GSK audit or regulatory inspection) and must be available for review in conjunction with assessment of the facility, supporting systems, and relevant site staff.

Where permitted by local laws/regulations or institutional policy, some or all of the records may be maintained in a format other than hard copy (e.g., microfiche, scanned, electronic); however, caution must be exercised before such action is taken. The investigator must ensure that all reproductions are legible and are a true and accurate copy of the original. In addition, they must meet accessibility and retrieval standards, including regeneration of a hard copy, if required. The investigator must also ensure that an acceptable back-up of the reproductions exists and that there is an acceptable quality control procedure in place for creating the reproductions.

GSK will inform the investigator of the time period for retaining the site records in order to comply with all applicable regulatory requirements. The minimum retention time will meet the strictest standard applicable to a particular site, as dictated by local laws/regulations, GSK standard operating procedures, and/or institutional requirements.

The investigator must notify GSK of any changes in the archival arrangements, including, but not limited to archival of records at an off-site facility or transfer of ownership of the records in the event that the investigator is no longer associated with the site.

14.8. Provision of Study Results to Investigators, Posting of Information on Publicly Available Clinical Trials Registers and Publication

Where required by applicable regulatory requirements, an investigator signatory will be identified for the approval of the clinical study report. The investigator will be provided reasonable access to statistical tables, figures, and relevant reports and will have the opportunity to review the complete study results at a GSK site or other mutually-agreeable location.

GSK will also provide the investigator with the full summary of the study results. The investigator is encouraged to share the summary results with the study subjects, as appropriate.

The results summary will be posted to the GSK Clinical Study Register no later than 8 months after the final primary completion date, the date that the final subject was examined or received an intervention for the purposes of final collection of data for the primary outcome. In addition, a manuscript will be submitted to a peer reviewed journal

for publication no later than 18 months after the LSLV. When manuscript publication in a peer-reviewed journal is not feasible, a statement will be added to the register to explain the reason for not publishing.

16. APPENDICES

16.1. Appendix 1: Liver Chemistry Monitoring, Interruption Stopping and Follow-up Criteria

Phase I Liver Safety Algorithm

16.2. Appendix 2: Country Specific Requirements

Specific QTc Stopping Criteria:

If specified by local requirements, a subject that meets the criteria QTc¹ below will have study treatment withheld:

The QT interval corrected for heart rate by Bazett's formula (QTcB) > 500 msec
--

¹Based on average corrected QT (QTc) interval value of triplicate ECGs to include manual over-read. For example, if an ECG demonstrates a prolonged QT interval, obtain 2 more ECGs over a brief period, and then use the averaged QTc values of the 3 ECGs to determine whether the subjects should have study treatment withheld.

[figure not shown]
In addition, for subjects in designated countries, study treatment must be withheld for an increase in QTc >60 msec from baseline.

If the QTc prolongation resolves to Grade 1 or baseline, the subject may be re-started on the study treatment if the investigator and GSK Medical Monitor agree that the subject will benefit from further treatment.

No other known country specific requirements are currently required.

16.3. Appendix 3: ECOG Performance Status

CCI - This section contained Clinical Outcome Assessment data collection questionnaires or indices, which are protected by third party copyright laws and therefore have been excluded.

16.4. Appendix 4: Estimated Glomerular Filtration Rate Using the Modification of Diet in Renal Disease (MDRD) Equation

Background

The Modification of Diet in Renal Disease (MDRD) equation provides an estimate of glomerular filtration rate (GFR), using values for a subject's serum creatinine, age, sex, and race (Levey, 1999).

MDRD Equation when creatinine is expressed in mg/dL:

$$\text{Estimated GFR (ml/min/1.73 m}^2\text{)} = 186 \times (\text{serum creatinine})^{-1.154} \times (\text{age})^{-0.203} \times (0.742 \text{ if female}) \times (1.212 \text{ if black})$$

MDRD Equation when creatinine is expressed in $\mu\text{mol/L}$:

$$\text{Estimated GFR (ml/min/1.73 m}^2\text{)} = 32788 \times (\text{serum creatinine})^{-1.154} \times (\text{age})^{-0.203} \times (0.742 \text{ if female}) \times (1.212 \text{ if black})$$

Reference

Glomerular Filtration Rate Interpretation

Table 16 Kidney function using GFR estimates

Stage	GFR	Equation (age in years for ≥ 18)
1	90+	Normal kidney function
2	60 - 89	Mildly reduced kidney function
3	30 - 59	Moderately reduced kidney function
4	15 - 29	Severely reduced kidney function
5	<15	Very severe, or endstage kidney failure

Website to calculate the glomerular filtration rate

http://nephron.org/MDRD_GFR.cgi

16.5. Appendix 5: RECIST 1.1 Guidelines for Evaluation of Disease

Measurable and Non-measurable Definitions

Measurable lesion:

A non nodal lesion that can be accurately measured in at least one dimension (longest dimension) of

- ≥ 10 mm with MRI or CT when the scan slice thickness is no greater than 5 mm. If the slice thickness is greater than 5 mm, the minimum size of a measurable lesion must be at least double the slice thickness (e.g., if the slice thickness is 10 mm, a measurable lesion must be ≥ 20 mm).
- ≥ 10 mm caliper/ruler measurement by clinical exam or medical photography.
- ≥ 20 mm by chest x-ray.

Additionally lymph nodes can be considered pathologically enlarged and measurable if

- ≥ 15 mm in the short axis when assessed by CT or MRI (slice thickness recommended to be no more than 5 mm). At baseline and follow-up, only the short axis will be measured [[Eisenhauer, 2009](#)].

Non-measurable lesion:

All other lesions including lesions too small to be considered measurable (longest diameter < 10 mm or pathological lymph nodes with ≥ 10 mm and < 15 mm short axis) as well as truly non-measurable lesions, which include: leptomeningeal disease, ascites, pleural or pericardial effusions, inflammatory breast disease, lymphangitic involvement of the skin or lung, abdominal masses/abdominal organomegaly identified by physical exam that is not measurable by reproducible imaging techniques [[Eisenhauer, 2009](#)].

Measurable disease: The presence of at least one measurable lesion. Palpable lesions that are not measurable by radiologic or photographic evaluations may not be utilized as the only measurable lesion.

Non-Measurable only disease: The presence of only non-measurable lesions.

Response Criteria

Evaluation of target lesions

Definitions for assessment of response for target lesion(s) are as follows:

- CR: Disappearance of all target lesions. Any pathological lymph nodes must be < 10 mm in the short axis.
- PR: At least a 30% decrease in the sum of the diameters of target lesions, taking as a reference, the baseline sum of the diameters (e.g., percent change from baseline).

- SD: Neither sufficient shrinkage to qualify for PR nor sufficient increase to qualify for PD.
- PD: At least a 20% increase in the sum of the diameters of target lesions, taking as a reference, the smallest sum of diameters recorded since the treatment started (e.g., percent change from nadir, where nadir is defined as the smallest sum of diameters recorded since treatment start). In addition, the sum must have an absolute increase from nadir of 5 mm.
- Not Applicable (NA): No target lesions at baseline.
- Not Evaluable (NE): Cannot be classified by one of the five preceding definitions.

NOTE:

- If lymph nodes are documented as target lesions the short axis is added into the sum of the diameters (e.g., sum of diameters is the sum of the longest diameters for non-nodal lesions and the short axis for nodal lesions). When lymph nodes decrease to non-pathological size (short axis <10 mm) they should still have a measurement reported in order not to overstate progression.
- If at a given assessment time point all target lesions identified at baseline are not assessed, sum of the diameters cannot be calculated for purposes of assessing CR, PR, or SD, or for use as the nadir for future assessments. However, the sum of the diameters of the assessed lesions and the percent change from nadir should be calculated to ensure that progression has not been documented. If an assessment of PD cannot be made, the response assessment should be NE.
- All lesions (nodal and non-nodal) should have their measurements recorded even when very small (e.g., 2 mm). If lesions are present but too small to measure, 5 mm should be recorded and should contribute to the sum of the diameters, unless it is likely that the lesion has disappeared in which case 0 mm should be reported.
- If a lesion disappears and reappears at a subsequent time point it should continue to be measured. The response at the time when the lesion reappears will depend upon the status of the other lesions. For example, if the disease had reached a CR status then PD would be documented at the time of reappearance. However, if the response status was PR or SD, the diameter of the reappearing lesion should be added to the remaining diameters and response determined based on percent change from baseline and percent change from nadir.

Evaluation of non-target lesions

Definitions for assessment of response for non-target lesions are as follows:

- CR: The disappearance of all non-target lesions. All lymph nodes identified as a site of disease at baseline must be non-pathological (e.g., <10 mm short axis).
- Non-CR/Non-PD: The persistence of 1 or more non-target lesion(s) or lymph nodes identified as a site of disease at baseline ≥ 10 mm short axis.
- PD: Unequivocal progression of existing non-target lesions.
- Not Applicable (NA): No non-target lesions at baseline.

- Not Evaluable (NE): Cannot be classified by one of the four preceding definitions.

NOTE:

- In the presence of measurable disease, progression on the basis of solely non-target disease requires substantial worsening such that even in the presence of SD or PR in target disease, the overall tumor burden has increased sufficiently to merit discontinuation of therapy.
- In the presence of non-measurable only disease consideration should be given to whether or not the increase in overall disease burden is comparable in magnitude to the increase that would be required to declare PD for measurable disease.
- Sites of non-target lesions, which are not assessed at a particular timepoint based on the assessment schedule, should be excluded from the response determination (e.g., non-target response does not have to be "Not Evaluable").

New lesions

New malignancies denoting disease progression must be unequivocal. Lesions identified in follow-up in an anatomical location not scanned at baseline are considered new lesions.

Any equivocal new lesions should continue to be followed. Treatment can continue at the discretion of the investigator until the next scheduled assessment. If at the next assessment the new lesion is considered to be unequivocal, progression should be documented.

Evaluation of overall response

Table 17 presents the overall response at an individual time point for all possible combinations of tumor responses in target and non-target lesions with or without the appearance of new lesions for subjects with measurable disease at baseline.

Table 17 Evaluation of Overall Response for Subjects with Measurable Disease at Baseline

Target Lesions	Non-Target Lesions	New Lesions	Overall Response
CR	CR or NA	No	CR
CR	Non-CR/Non-PD or NE	No	PR
PR	Non-PD or NA or NE	No	PR
SD	Non-PD or NA or NE	No	SD
NE	Non-PD or NA or NE	No	NE
PD	Any	Yes or No	PD
Any	PD	Yes or No	PD
Any	Any	Yes	PD

CR=complete response, PR = partial response, SD=stable disease, PD=progressive disease, NA= Not applicable, and NE=Not Evaluable

Table 18 presents the overall response at an individual time point for all possible combinations of tumor responses in non-target lesions with or without the appearance of new lesions for subjects with non-measurable only disease at baseline.

Table 18 Evaluation of Overall Response for Subjects with Non-Measurable Only Disease at Baseline

Non-Target Lesions	New Lesions	Overall Response
CR	No	CR
Non CR/Non PD	No	Non CR/Non PD
NE	No	NE
Unequivocal PD	Yes or No	PD
Any	Yes	PD

CR=complete response, PD=progressive disease, and NE=Not Evaluable

NOTE:

- Subjects with a global deterioration of health status requiring discontinuation of treatment without objective evidence of disease progression at that time should be classified as having "symptomatic deterioration." Objective response status is determined by evaluations of disease burden. Every effort should be made to document the objective progression even after discontinuation of treatment.
- In some circumstances, it may be difficult to distinguish residual disease from normal tissue. When the evaluation of CR depends on this determination, it is recommended that the residual lesion be investigated (fine needle aspirate/biopsy) to confirm the CR.

Evaluation of best overall response

The best overall response is the best response recorded from the start of the treatment until disease progression/recurrence and will be determined programmatically by GSK based on the investigators assessment of response at each time point.

- To be assigned a status of SD, follow-up disease assessment must have met the SD criteria at least once after first dose at a minimum interval of 8 weeks.
- If the minimum time for SD is not met, best response will depend on the subsequent assessments. For example if an assessment of PD follows the assessment of SD and SD does not meet the minimum time requirement the best response will be PD. Alternative subjects lost to follow-up after an SD assessment not meeting the minimum time criteria will be considered not evaluable.

Confirmation Criteria:

To be assigned a status of PR or CR, a confirmatory disease assessment should be performed no less than 4 weeks (28 days) after the criteria for response are first met.

References:

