7.8. Evaluation of Anti-Cancer Activity

Disease assessment may include imaging (e.g., CT scan, MRI, bone scan, plain radiography) and physical examination (as indicated for palpable/superficial lesions). Disease assessment will be completed within 4 weeks prior to the first dose of GSK2849330, then every 8 or 9 weeks thereafter, and at the final study visit. See the Time and Events Tables (Section 7.1) for the schedule of assessments of anti-cancer activity. Assessments must be performed on a calendar schedule and should not be affected by dose interruptions/delays. For post-baseline assessments, a window of ± 7 days is permitted to allow for flexible scheduling. If the last radiographic assessment was more than 8 weeks prior to the subject's withdrawal from study, progressive disease (PD) has not been documented, and the subject has not started subsequent anti-cancer therapy, a disease assessment should be obtained at the Follow-up visit or the Post-study visit.

In addition to the above, a MRI with contrast should be considered to rule out the presence of brain metastases. CT scans with and without contrast may be performed if a MRI is contraindicated or otherwise unavailable.

For purposes of determining futility, disease progression and response evaluations will be determined according to the definitions established in the Response Evaluation Criteria in Solid Tumors (RECIST 1.1) [Eisenhauer, 2009] (see Appendix 5). Exploratory assessment of response according to immune-related response criteria (Appendix 6) and mRECIST (Appendix 7) [Lencioni, 2010] should also be recorded. Subjects whose disease responds (either CR or PR) should have a confirmatory disease assessment performed at least 4 weeks after the date of assessment during which the response was demonstrated. More frequent disease assessments may be performed at the discretion of the investigator. To ensure comparability between the baseline and subsequent assessments, the same method of assessment, the same technique and the same radiologist should be used when assessing response. Images should be retained until study completion to facilitate central review if requested. Tumor markers should be followed serially per institutional guidelines and recorded in the eCRF where part of standard practice.

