# 19.1.2. Efficacy Figures and Tables

# Tables

No.	Population	IDSL / TST ID / Example Shell	Title	Programming Notes	Deliverable
10.1	All Treated	RE1a	Summary of Investigator Assessed Best Response (RECIST 1.1 Criteria)	Best Resp. only	SAC
10.2	All Treated	RE5	Listing of Investigator-Assessed Tumor Responses (RECIST1.1 Criteria)		SAC
10.3	All Treated	LA2	Listing of Target Lesion (RECIST v1.1)		SAC
10.4	All Treated	LA3	Listing of Non-target Lesion (RECIST v1.1)		SAC

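### The 8-week minimum for stable disease ignores the 7-day early scan window, so a compliant early SD may end up as PD or not evaluable

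*Protocol*

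**What the plan says.** Three rules meet here.

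- **Scan timing (protocol Section 7.8).** Disease is assessed before treatment, "then every 8 or 9 weeks thereafter, and at the final study visit". The timing is tied to the calendar: "Assessments must be performed on a calendar schedule and should not be affected by dose interruptions/delays". The tolerance is explicit: "For post-baseline assessments, a window of ± 7 days is permitted to allow for flexible scheduling". The Time and Events tables use the 8-week interval for weekly and 2-weekly dosing in Part 1 and for all of Part 2 (Table 12). Only the 3-weekly PK/PD cohorts (Table 11) use 9 weeks.
- **Minimum for SD (protocol Appendix 5, best overall response).** To count as SD, a follow-up assessment "must have met the SD criteria at least once after first dose at a minimum interval of 8 weeks". No allowance is made for the scan window. Best response is to be derived by program from the investigator's time-point assessments.
- **What follows if the minimum is missed (same place).** Later assessments decide. Two outcomes are spelled out: "if an assessment of PD follows the assessment of SD and SD does not meet the minimum time requirement the best response will be PD", and subjects "lost to follow-up after an SD assessment not meeting the minimum time criteria will be considered not evaluable".

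The SAP does not restate the SD minimum or give a best-response algorithm. Its Section 8.1 defines no assessment windows, and its Section 9.2.3 counts efficacy days from actual dates. Best response is summarised in Table 10.1 (SAP Section 19.1.2).

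**The concern.** The scan rule and the classification rule use the same 8-week mark, but only the first has a tolerance. A site can follow the schedule correctly and still produce an SD scan that the classification rule will not accept.

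Take two subjects with the same course, SD at the first scan and PD at the second. One is first scanned 56 days after first dose and the other at 54 days, both within the window. Read literally, the first has best response SD and the second PD. The difference comes from the scan date alone.

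The SD, PD and not-evaluable rows of Table 10.1 are at stake. It is the only efficacy summary table in the SAP's display list; Tables 10.2 to 10.4 are listings. Any benefit measure that counts SD would be affected in the same way. The error runs in one direction: the rule can remove SDs but cannot create them.

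**Working it through.** The plan states no figure for this point, so there is nothing to reproduce. The check is a day count.

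**Inputs.** The SD minimum is 8 weeks = 56 days after first dose (Appendix 5). The first scan is due at day 56 or day 63, within 7 days either way (Section 7.8). The narrower continuation-visit windows of 2 or 3 days in the Time and Events tables serve as a sensitivity check. SAP Section 9.2.4 calculates durations as stop minus start plus one, so a scan 55 days after first dose has duration 56 and would pass.

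**Day count.** Permitted days run from (due day − window) to (due day + window). A day fails if it is below 56, or if day + 1 is below 56 under the plus-one convention.

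| First scan and window | Permitted days after first dose | Fail | Fail, plus-one |
|---|---|---|---|
| 8 weeks, ±7 days (Section 7.8) | 49-63 | 7 of 15 (days 49-55) | 6 of 15 |
| 8 weeks, ±3 days (Tables 7, 9) | 53-59 | 3 of 7 | 2 of 7 |
| 8 weeks, ±2 days (Tables 8, 10, 12) | 54-58 | 2 of 5 | 1 of 5 |
| 9 weeks, ±7 days (Section 7.8) | 56-70 | 0 of 15 | 0 of 15 |

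Narrower windows shrink the mismatch on the 8-week schedule but do not remove it. The 9-week schedule escapes because its earliest permitted scan falls on day 56.

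**Number of subjects (illustration).** Reclassified subjects = n × P(first scan too early) × P(SD at first scan) × P(next assessment is PD or absent). The documents give none of these probabilities. Assume scan days spread evenly over the window (7/15 = 0.467), SD in 40% at first scan, and 25-75% for the last factor.

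- Ceiling, with the last factor set to 1: 0.467 × 0.4 × 12 = 2.2 per 12; 0.467 × 0.4 × 30 = 5.6 per 30.
- With the last factor at 0.25 to 0.75: 2.24 × 0.25 = 0.6 to 2.24 × 0.75 = 1.7 per 12; 5.6 × 0.25 = 1.4 to 5.6 × 0.75 = 4.2 per 30.
- With SD at first scan at 20% or 60%, the ceilings become 1.1 or 3.4 per 12, and 2.8 or 8.4 per 30.

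The values 12 and 30 are the minimum and maximum Part 2 group sizes, used here only for scale.

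**Response rate and futility.** Moving a subject among SD, PD and not evaluable leaves the number of CRs and PRs unchanged. SAP Section 9.1 keeps not-evaluable subjects in the denominator as non-responders, so ORR does not change. The futility boundaries in protocol Table 15 count responders, so they are unaffected too if a responder is a CR or PR.

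**The case against.** The case against rests on consequence, since the two rules plainly differ.

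- **Most early SDs may be rescued.** A reader might infer that every SD on days 49-55 becomes PD or not evaluable. Appendix 5 does not say that. A later SD at or after 8 weeks, or a later confirmed PR or CR, decides the best response. Only an early SD followed directly by PD, or by no further qualifying assessment, is lost. This stands, and it is why the ceiling figures are not estimates.
- **The not-evaluable route is partly closed.** Footnote 21 of the Time and Events tables requires an assessment at Follow-up or Post-study for subjects who stop before progression, and SD there past 8 weeks would qualify. This stands in part. Section 7.8 asks for that scan only when the last one was more than 8 weeks before withdrawal, and subjects truly lost have none.
- **The program may not apply the rule literally.** SAP Section 9.2 leaves full derivations to separate dataset specifications, and Section 9.2.8 reports data by nominal visit. If the minimum were applied to the nominal Week 8 visit, the problem would disappear. Neither document says so for SD, so this leaves the programmed result uncertain. It does not settle the point.
- **Little depends on it.** The primary objective is safety, the SAP abbreviates the efficacy analysis because the study stopped early, and Tables 10.2 to 10.4 keep each early SD visible. This stands as a limit on importance.

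**Conclusion.** The two rules are inconsistent as written. On the 8-week schedule, SD on 7 of the 15 permitted first-scan days (6 of 15 with the plus-one convention) does not meet the SD minimum; on the 9-week schedule none fails. The result can only be fewer SDs in Table 10.1 and in any measure built on SD.

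The size is modest: about 0.6-1.7 per 12 or 1.4-4.2 per 30 subjects on the 8-week schedule, with a ceiling of about 2 per 12 or 6 per 30. These figures rest on the assumed even spread of scan days, 40% SD at first scan and a 25-75% chance that the next assessment is PD or absent.

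Three stronger readings are not supported:

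- **That 2 of 12 or 6 of 30 in each tumour group will be misclassified.** Those are ceilings. SAP Section 11 reports best response by dose group and overall, and SAP Section 7.1 gives Part 2 a single column.
- **That a disease control endpoint is biased.** Neither document defines one. Protocol Section 13.1.2 calls the tested quantity a clinical benefit rate without defining it, which is a separate gap. If SD were counted in it, the downward effect would carry over.
- **That ORR or the futility decision is distorted.** They are not, provided response means CR or PR.

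**What to change.** In Appendix 5 and in the best-response dataset specification, set the SD minimum to 8 weeks minus the permitted window: 49 days after first dose, which is Study Day 50 under SAP Section 9.2.3. State the day-count convention alongside it. Then 0 of the 15 permitted days fail.

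The change is one number in each place and needs no new scans or data. ORR and the futility boundaries stay as they are if response means CR or PR. The cost is a slightly shorter SD requirement. If the intention was to judge the minimum on the nominal visit, writing that down would also resolve the mismatch. Making the window one-sided would keep a strict 8 weeks, but gives up scheduling flexibility and cannot help scans already done.
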